13.3 Analysis of Secondary Endpoints

We will assess pMET (1235/1356) reduction, MET reduction, VEGF reduction, TSP-1 increase, HIF1 α increase, and change in EMT markers, descriptively (magnitude of change, with 2-sided 90% CI), in blood and tumor assays (where paired samples are available), for the various dose combinations in the escalation and expansion phases.

13.4 Reporting and Exclusions

13.4.1 Evaluation of toxicity – All patients will be evaluable for toxicity from the time of their first treatment with study agents.

13.4.2 Evaluation of response – All patients included in the study will be assessed for response to treatment, even if there are major protocol treatment deviations or if they are ineligible. Each patient will be assigned one of the following categories: 1) complete response, 2) partial response, 3) stable disease, 4) progressive disease, 5) early death from malignant disease, 6) early death from toxicity, 7) early death because of other cause, or 9) unknown (not assessable, insufficient data). [Note: By arbitrary convention, category 9 usually designates the “unknown” status of any type of data in a clinical database.]

All of the patients who met the eligibility criteria (with the possible exception of those who received no study medication) will be included in the main analysis of the response rate. Patients in response categories 4-9 will be considered to have a treatment failure (disease progression). Thus, an incorrect treatment schedule or drug administration does not result in exclusion from the analysis of the response rate. Precise definitions for categories 4-9 will be protocol specific.

All conclusions will be based on all eligible patients. Subanalyses may then be performed on the basis of a subset of patients, excluding those for whom major protocol deviations have been identified (e.g., early death due to other reasons, early discontinuation of treatment, major protocol violations, etc.). However, these subanalyses may not serve as the basis for drawing conclusions concerning treatment efficacy, and the reasons for excluding patients from the analysis will be clearly reported. The 95% confidence intervals will also be provided.

14 HUMAN SUBJECTS PROTECTIONS

14.1 Justification for Subject Selection

This study will be open to all individuals regardless of gender, ethnicity, or race, provided that the aforementioned inclusion and exclusion criteria are met. Patients for this study will be recruited through internal referral, our physician referral base, and through various cancer information hotlines (i.e., Clinical Studies Support Center, [name]). To date, there is no information that suggests that differences in drug metabolism or effect on tumor would be expected in one ethnic group compared to another. Efforts will be made to extend accrual to each representative population, but a balance must be struck between participant safety considerations and limitations on the number of individuals exposed to potentially ineffective treatments on the one hand and the need to explore racial/ethnic aspects of clinical research on the other hand. If differences in outcome that correlate to ethnic identity are noted, a follow-up study may be written to investigate those differences more fully.

Due to lack of knowledge of the effects of pazopanib and ARQ 197 on the fetus or infants, as well as the possibility of teratogenic effects, pregnant and nursing women will be excluded from this trial. Patients with unstable or serious medical conditions are excluded due to the possibility that pazopanib and/or ARQ 197 may worsen their condition and the likelihood that the underlying condition may obscure the attribution of adverse events with respect to pazopanib and/or ARQ 197. HIV-positive patients on combination antiretroviral therapy are excluded from the study because of possible PK interactions with pazopanib and/or ARQ 197.

14.1.1 Participation of Children

This study includes patients 18 years of age and older. Because insufficient dosing or adverse event data are currently available on the use of pazopanib and ARQ 197 in patients <18 years of age, children are excluded from this study, but may be eligible for future pediatric trials. Studies will be performed in patients <18 years of age when it is appropriate to do so.

14.2 Evaluation of Benefits and Risks/Discomforts

There may or may not be any clinical benefit to a patient from participation in this trial. Their participation will benefit future cancer patients. Potential risks include the possible occurrence of any of a range of side effects that are listed in the consent document. The procedure for protecting against or minimizing risks will be to medically evaluate patients as described in Sections 5 and 6. Although no compensation is available, any injury will be fully evaluated and treated in keeping with the benefits or care to which participants are entitled under applicable regulations.

14.3 Consent and Assent Process and Documentation

An associate or principal investigator on the trial will inform patients of the purpose, alternatives, drug administration plan, research objectives, and follow-up of this trial. The patient will be provided an IRB-approved consent for review and signature and his/her questions will be

answered. After a decision is made to enroll into the study, a signature will be obtained from the patient. The original signed consent goes to Medical Records; a copy will be placed in the research record.

All patients must have a signed informed consent form and an on-study (confirmation of eligibility) form filled out and signed by a participating investigator before entering on study.

14.4 Procedure for Protecting Against or Minimizing Any Potential Risks

All care will be taken to minimize side effects, but they can be unpredictable in nature and severity. This study may involve risks to patients, which are currently unforeseeable. All patients will be monitored for side effects from taking study medication. This research represents a greater than minimal risk to participants, but presents the prospect of direct benefit to individual subjects.

The research component of this study required to obtain 2 CT tumor biopsies confers radiation exposure at an effective dose of 0.29 rem. This dose is below NIH RSC guidelines and represents a slightly greater than minimal risk to patients.

APPENDIX A: PERFORMANCE STATUS CRITERIA

ECOG Performance Status Scale	
Grade	Descriptions
0	Normal activity. Fully active, able to carry on all pre-disease performance without restriction.
1	Symptoms, but ambulatory. Restricted in physically strenuous activity, but ambulatory and able to carry out work of a light or sedentary nature (e.g., light housework, office work).
2	In bed <50% of the time. Ambulatory and capable of all self-care, but unable to carry out any work activities. Up and about more than 50% of waking hours.
3	In bed >50% of the time. Capable of only limited self-care, confined to bed or chair more than 50% of waking hours.
4	100% bedridden. Completely disabled. Cannot carry on any self-care. Totally confined to bed or chair.
5	Dead.

APPENDIX B: POTENTIAL DRUG INTERACTIONS

CYP2C19 Inhibitors

Amiodarone	Felbamate	Methoxsalen	Ritonavir
Amitriptyline	Fenofibrate	Methsuximide	Rosiglitazone
Amprenavir	Fluconazole	Miconazole	Saquinavir
Aprepitant	Fluoxetine	Moclobemide	Selegiline
Azelastine	Fluvoxamine	Modafinil	Sertraline
Bortezomib	Fosamprenavir	Nelfinavir	Sildenafil
Buprenorphine	Gefitinib	Nicardipine	Sulconazole
Cholecalciferol/Vitamin D ₃	Gemfibrozil	Nilutamide	Telmisartan
Cimetidine	Imipramine	Olanzapine	Ticlopidine
Citalopram	Indinavir	Omeprazole	Tioconazole
Clotrimazole	Indomethacin	Orphenadrine	Topiramate
Clozapine	Isoniazid	Oxcarbazepine	Torsemide
Delavirdine	Ketoconazole	Paroxetine	Tranlycypromine
Diazepam	Lansoprazole	Pentamidine	Valdecoxib
Dimethyl sulfoxide	Letrozole	Pimozide	Valproic acid
Drospirenone	Loratadine	Pioglitazone	Voriconazole
Efavirenz	Losartan	Probenecid	Warfarin
Entacapone	Mephobarbital	Progesterone	Zafirlukast
Ethinyl estradiol	Mestranol	Propofol	
Ethotoin	Methimazole	Rabeprazole	

CYP2C19 Inducers

Aminoglutethimide	Fosphenytoin	Rifampin	St. John's wort (1)
Carbamazepine	Phenytoin		

CYP2C19 Substrates

Carisoprodol	Escitalopram	Methsuximide	Phenobarbital
Cilostazol	Esomeprazole	Moclobemide	Phenytoin
Citalopram	Fosphenytoin	Nelfinavir	Progesterone
Clobazam	Imipramine	Nilutamide	Rabeprazole
Clomipramine	Lansoprazole	Omeprazole	Sertraline
Desogestrel	Mephenytoin	Pantoprazole	Trimipramine
Diazepam	Mephobarbital	Pentamidine	Voriconazole

When ARQ 197 is co-administered with compounds classified as 'inhibitors', increased plasma concentrations of ARQ 197 is the potential outcome. The co-administration of 'inducers' would potentially lower plasma ARQ 197 concentrations. When drugs classified as 'substrates' are co-administered with ARQ 197, there is the potential for higher concentrations of the 'substrate'.

Note: Adapted from Cytochrome P450 Enzymes: Substrates, Inhibitors, and Inducers. In: Lacy CF, Armstrong LL, Goldman MP, Lance LL eds. Drug Information Handbook 15TH ed. Hudson, OH; LexiComp Inc. 2007: 1899-1912.

Only major substrates and effective inducers are listed.

Additional information for drug interactions with cytochrome P450 isoenzymes can be found at <http://medicine.iupui.edu/flockhart/>.

(1) Wang *et al.* (2004). *Clin Pharmacol Ther.* 75:191-197

CYP3A4 Inhibitors

Acetaminophen	Cyclosporine	Glyburide	Modafinil	Ranolazine
Acetazolamide	Danazol	Grapefruit juice (2)	Nefazodone	Risperidone
Amiodarone	Dasatinib (1)	Haloperidol	Nelfinavir	Ritonavir
Amlodipine	Delavirdine	Hydralazine	Nevirapine	Saquinavir
Amprenavir	Desipramine	Ifosfamide	Nicardipine	Selegiline
Anastrozole	Dexmedetomidine	Imatinib	Nifedipine	Sertraline
Aprepitant	Diazepam	Indinavir	Nisoldipine	Sildenafil
Atazanavir	Diclofenac	Irbesartan	Nizatidine	Sirolimus
Atorvastatin	Dihydroergotamine	Isoniazid	Norfloxacin	Sulconazole
Azelastine	Diltiazem	Isradipine	Olanzapine	Tacrolimus
Azithromycin	Disulfiram	Itraconazole	Omeprazole	Tamoxifen
Betamethasone	Docetaxel	Ketoconazole	Orphenadrine	Telithromycin
Bortezomib	Doxorubicin	Lansoprazole	Oxybutynin	Teniposide
Bromocriptine	Doxycycline	Lidocaine	Paroxetine	Testosterone
Caffeine	Drospirenone	Lomustine	Pentamidine	Tetracycline
Cerivastatin	Efavirenz	Losartan	Pergolide	Ticlopidine
Chloramphenicol	Enoxacin	Lovastatin	Phencyclidine	Tranlycypromine
Chlorzoxazone	Entacapone	Mefloquine	Pilocarpine	Trazodone
Cimetidine	Ergotamine	Mestranol	Pimozide	Troleandomycin
Ciprofloxacin	Erythromycin	Methadone	Pravastatin	Valproic acid
Cisapride	Ethinyl estradiol	Methimazole	Prednisolone	Venlafaxine
Clarithromycin	Etoposide	Methoxsalen	Primaquine	Verapamil
Clemastine	Felodipine	Methylprednisolone	Progesterone	Vinblastine
Clofazimine	Fentanyl	Metronidazole	Propofol	Vincristine
Clotrimazole	Fluconazole	Miconazole	Propoxyphene	Vinorelbine
Clozapine	Fluoxetine	Midazolam	Quinidine	Voriconazole
Cocaine	Fluvastatin	Mifepristone	Quinine	Zafirlukast
Conivaptan	Fluvoxamine	Mirtazapine	Quinupristin	Ziprasidone
Cyclophosphamide	Fosamprenavir	Mitoxantrone	Rabeprazole	

CYP3A4 Inducers

Aminoglutethimide	Nafcillin	Pentobarbital	Primidone	Rifapentine
Carbamazepine	Nevirapine	Phenobarbital	Rifabutin	St. John's wort (3)
Fosphenytoin	Oxcarbazepine	Phenytoin	Rifampin	

CYP3A4 Substrates

Albuterol	Docetaxel	Ketoconazole	Quetiapine
Alfentanil	Doxepin	Lansoprazole	Quinidine
Alprazolam	Doxorubicin	Letrozole	Rabeprazole
Amlodipine	Doxycycline	Levomethadyl acetate hydrochloride	Repaglinide
Amprenavir	Efavirenz	Levonorgestrel	Rifabutin
Aprepitant	Eletriptan	Lidocaine	Rifampin
Aripiprazole	Enalapril	Losartan	Ritonavir
Atazanavir	Eplerenone	Lovastatin	Saquinavir
Atorvastatin	Ergoloid mesylates	Medroxyprogesterone	Sertraline
Benzphetamine	Ergonovine	Mefloquine	Sibutramine
Bisoprolol	Ergotamine	Mestranol	Sildenafil
Bortezomib	Erythromycin	Methadone	Simvastatin
Bosentan	Escitalopram	Methylergonovine	Sirolimus
Bromazepam	Estradiol	Methysergide	Sufentanil
Bromocriptine	Estrogens, conj., synthetic	Miconazole	Tacrolimus
Buprenorphine	Estrogens, conj., equine	Midazolam	Tamoxifen
Buspiron	Estrogens, conj., esterified		Tamsulosin

Busulfan	Estrone	Miglustat	Telithromycin
Carbamazepine	Estropipate	Mirtazapine	Teniposide
Cerivastatin	Ethinyl estradiol	Modafinil	Terbinafine
Chlordiazepoxide	Ethosuximide	Montelukast	Tetracycline
Chloroquine	Etoposide	Moricizine	Theophylline
Chlorpheniramine	Felbamate	Nateglinide	Tiagabine
Cisapride	Felodipine	Nefazodone	Ticlopidine
Citalopram	Fentanyl	Nelfinavir	Tolterodine
Clarithromycin	Flurazepam	Nevirapine	Toremifene
Clobazam	Flutamide	Nicardipine	Trazodone
Clonazepam	Fosamprenavir	Nifedipine	Triazolam
Clorazepate	Fulvestrant	Nimodipine	Trimethoprim
Cocaine	Gefitinib	Nisoldipine	Trimipramine
Colchicine	Halofantrine	Nitrendipine	Troleandomycin
Cyclophosphamide	Haloperidol	Norethindrone	Vardenafil
Cyclosporine	Ifosfamide	Norgestrel	Venlafaxine
Dantrolene	Imatinib	Ondansetron	Verapamil
Dapsone	Indinavir	Paclitaxel	Vinblastine
Delavirdine	Irinotecan	Pergolide	Vincristine
Diazepam	Isosorbide dinitrate	Phencyclidine	Vinorelbine
Digitoxin	Isosorbide mononitrate	Pimozide	Zolpidem
Dihydroergotamine	Isradipine	Pioglitazone	Zonisamide
Diltiazem	Itraconazole	Primaquine	Zopiclone
Disopyramide	Ketamine	Progesterone	

When pazopanib and ARQ 197 are co-administered with compounds classified as ‘inhibitors’, increased plasma concentrations of pazopanib and ARQ 197 are the potential outcomes. The co-administration of ‘inducers’ would potentially lower plasma concentrations of both study drugs. When drugs classified as ‘substrates’ are co-administered with pazopanib or ARQ 197, there is the potential for higher concentrations of the ‘substrate’.

Note: Adapted from Cytochrome P450 Enzymes: Substrates, Inhibitors, and Inducers. In: Lacy CF, Armstrong LL, Goldman MP, Lance LL eds. Drug Information Handbook 15TH ed. Hudson, OH; LexiComp Inc. 2007: 1899-1912.

Only major substrates and effective inducers are listed. Additional information for drug interactions with cytochrome P450 isoenzymes can be found at <http://medicine.iupui.edu/flockhart/>.

(1) Investigator’s Brochure: Pazopanib. GlaxoSmithKline. February 2009.

(2) Malhotra *et al.* (2001). Clin Pharmacol Ther. 69:14-23.

(3) Mathijssen *et al.* (2002). J Natl Cancer Inst. 94:1247-1249; Frye *et al.* (2004). Clin Pharmacol Ther. 76:323-329.

CYP2C8/9 Inhibitors

Amiodarone	Felodipine	Modafinil	Sertraline
Amitriptyline	Fluconazole	Montelukast	Sildenafil
Amlodipine	Fluoxetine	Nateglinide	Simvastatin
Anastrozole	Fluphenazine	Nelfinavir	Sulconazole
Aprepitant	Flurbiprofen	Nicardipine	Sulfadiazine
Atazanavir	Fluvastatin	Nifedipine	Sulfamethoxazole
Azelastine	Fluvoxamine	Olanzapine	Sulfinpyrazone
Bortezomib	Gemfibrozil	Omeprazole	Sulfisoxazole
Candesartan	Ibuprofen	Ondansetron	Tamoxifen
Chloramphenicol	Imatinib	Orphenadrine	Teniposide
Cholecalciferol (Vitamin D ₃)	Indinavir	Pantoprazole	Thioridazine
Cimetidine	Indomethacin	Paroxetine	Ticlopidine
Clopidogrel	Irbesartan	Pentamidine	Tioconazole
Clotrimazole	Isoniazid	Pioglitazone	Tolbutamide
Clozapine	Ketoconazole	Piroxicam	Tolcapone
Cyclosporine	Ketoprofen	Pravastatin	Tranlycypromine
Delavirdine	Lansoprazole	Progesterone	Tretinoin
Dexmedetomidine	Leflunomide	Propafenone	Triazolam
Diclofenac	Losartan	Propofol	Trimethoprim
Diltiazem	Lovastatin	Propoxyphene	Valdecoxib
Dimethyl sulfoxide	Mefenamic acid	Pyrimethamine	Valproic acid
Disulfiram	Meloxicam	Quinidine	Valsartan
Drospirenone	Methimazole	Quinine	Verapamil
Efavirenz	Methoxsalen	Ritonavir	Voriconazole
Entacapone	Metronidazole	Rosiglitazone	Warfarin
Eprosartan	Miconazole	Saquinavir	Zafirlukast
Etoposide	Midazolam	Selegiline	

CYP2C8/9 Inducers

Carbamazepine	Phenobarbital	Primidone	Rifapentine
Fosphenytoin	Phenytoin	Rifampin	Secobarbital

CYP2C8/9 Substrates

Alosetron	Losartan	Rifampin	Tolbutamide
Amiodarone	Mephenytoin	Rosiglitazone	Toremide
Bosentan	Mestranol	Selegiline	Trimethoprim
Carvedilol	Montelukast	Sertraline	Voriconazole
Fluoxetine	Nateglinide	Sulfadiazine	Warfarin
Fosphenytoin	Paclitaxel	Sulfamethoxazole	Zafirlukast
Glimepiride	Phenytoin	Sulfinpyrazone	Zopiclone
Glipizide	Pioglitazone	Sulfisoxazole	
Ketamine	Propofol	Tamoxifen	

When drugs classified as ‘substrates’ are co-administered with pazopanib, there is the potential for higher concentrations of the ‘substrate’. When pazopanib is co-administered with compounds classified as ‘inhibitors’, increased plasma concentrations of pazopanib is the potential outcome. The coadministration of ‘inducers’ would potentially lower plasma pazopanib concentrations.

(Adapted from Cytochrome P-450 Enzymes and Drug metabolism. In: Lacy CF, Armstrong LL, Goldman MP, Lance LL eds. Drug Information Handbook 12TH ed. Hudson, OH; LexiComp Inc. 2004: 1619-1631.)

CYP2D6 Substrates

Amitriptyline	Diphenhydramine	Maprotiline	Propranolol
Atomoxetine	Dolasetron	Metoclopramide	Protriptyline
Carvedilol	Doxepin	Metoprolol	Risperidone
Chlorpheniramine	Duloxetine	Mexiletine	Tamoxifen
Chlorpromazine	Flecainide	Nortriptyline	Thioridazine
Clomipramine	Fluoxetine	Palonosetron	Timolol
Codeine	Fluvoxamine	Paroxetine	Tolterodine
Desipramine	Haloperidol	Perhexiline	Tramadol
Dextromethorphan	Hydrocodone	Promethazine	Trazodone
Dihydrocodeine	Imipramine	Propafenone	Venlafaxine

When drugs classified as 'substrates' are co-administered with pazopanib, there is the potential for higher concentrations of the 'substrate'.

APPENDIX C: MEDICATIONS THAT MAY CAUSE QTc PROLONGATION

The following table presents a list of drugs that prolong, may prolong, or are unlikely to prolong the QTc. Please note that this list is frequently updated. For the most current list of medications, users should be directed to the following website: <http://www.azcert.org/medical-pros/drug-lists/drug-lists.cfm>.

Drugs that are generally accepted to have a risk of causing Torsades de Pointes	Drugs that in some reports have been associated with Torsades de Pointes and/or QTc prolongation but at this time lack substantial evidence for causing Torsades de Pointes	Drugs that, in some reports, have been weakly associated with Torsades de Pointes and/or QTc prolongation but that are unlikely to be a risk for Torsades de Pointes when used in usual recommended dosages and in subjects without other risk factors (e.g., concomitant QTc prolonging drugs, bradycardia, electrolyte disturbances, congenital long QTc syndrome, concomitant drugs that inhibit metabolism)
Generic/Brand Name	Generic/Brand Name	Generic/Brand Name
Amiodarone /Cordarone®	Alfuzosin /Uroxatral®	Amitriptyline /Elavil®
Amiodarone /Pacerone®	Amantadine /Symmetrel®	Ciprofloxacin /Cipro®
Arsenic trioxide /Trisenox®	Atazanavir /Reyataz®	Citalopram /Celexa®
Astemizole /Hismanal®	Azithromycin /Zithromax®	Clomipramine /Anafranil®
Bepidil /Vascor®	Chloral hydrate /Noctec®	Desipramine /Pertofrane®
Chloroquine /Aralen®	Clozapine /Clozaril®	Diphenhydramine /Benadryl®
Chlorpromazine /Thorazine®	Dolasetron /Anzemet®	Diphenhydramine /Nytol®
Cisapride /Propulsid®	Dronedarone /Multaq®	Doxepin /Sinequan®
Clarithromycin /Biaxin®	Felbamate /Felbatrol®	Fluconazole /Diflucan®
Disopyramide /Norpace®	Flecainide /Tambacor®	Fluoxetine /Sarafem®
Dofetilide /Tikosyn®	Foscarnet /Foscavir®	Fluoxetine /Prozac®
Domperidone /Motilium®	Fosphenytoin /Cerebyx®	Galantamine /Reminyl®
Droperidol /Inapsine®	Gatifloxacin /Tequin®	Imipramine /Norfranil®
Erythromycin /Erythrocin®	Gemifloxacin /Factive®	Itraconazole /Sporanox®
Erythromycin /E.E.S.®	Granisetron /Kytril®	Ketoconazole /Nizoral®
Halofantrine /Halfan®	Indapamide /Lozol®	Mexiletine /Mexitil®
Haloperidol /Haldol®	Isradipine /Dynacirc®	Nortriptyline /Pamelor®
Ibutilide /Corvert®	Lapatinib /Tykerb®	Paroxetine /Paxil®
Levomethadyl /Orlaam®	Lapatinib /Tyverb®	Protriptyline /Vivactil®
Mesoridazine /Serentil®	Levofloxacin /Levaquin®	Sertraline /Zoloft®

Drugs that are generally accepted to have a risk of causing Torsades de Pointes	Drugs that in some reports have been associated with Torsades de Pointes and/or QTc prolongation but at this time lack substantial evidence for causing Torsades de Pointes	Drugs that, in some reports, have been weakly associated with Torsades de Pointes and/or QTc prolongation but that are unlikely to be a risk for Torsades de Pointes when used in usual recommended dosages and in subjects without other risk factors (e.g., concomitant QTc prolonging drugs, bradycardia, electrolyte disturbances, congenital long QTc syndrome, concomitant drugs that inhibit metabolism)
Generic/Brand Name	Generic/Brand Name	Generic/Brand Name
Methadone /Dolophine®	Lithium /Lithobid®	Solifenacin /VESicare®
Methadone /Methadose®	Lithium /Eskalith®	Trimethoprim-Sulfa /Sulfa®
Pentamidine /Pentam®	Moexipril/HCTZ /Uniretic®	Trimethoprim-Sulfa /Bactrim®
Pentamidine /NebuPent®	Moxifloxacin /Avelox®	Trimipramine /Surmontil®
Pimozide /Orap®	Nicardipine /Cardene®	
Probucol /Lorelco®	Nilotinib /Tasigna®	
Procainamide /Pronestyl®	Octreotide /Sandostatin®	
Procainamide /Procan®	Ofloxacin /Floxin®	
Quinidine /Cardioquin®	Ondansetron /Zofran®	
Quinidine /Quinaglute®	Oxytocin /Pitocin®	
Sotalol /Betapace®	Paliperidone /Invega®	
Sparfloxacin /Zagam®	Perflutren lipid microspheres /Definity®	
Terfenadine /Seldane®	Quetiapine /Seroquel®	
Thioridazine /Mellaril®	Ranolazine /Ranexa®	
	Risperidone /Risperdal®	
	Roxithromycin* /Rulide®	
	Sertindole /Serlect®	
	Sertindole /Serdolect®	
	Sunitinib /Sutent®	
	Tacrolimus /Prograf®	
	Tamoxifen /Nolvadex®	
	Telithromycin /Ketek®	
	Tizanidine /Zanaflex®	
	Vardenafil /Levitra®	
	Venlafaxine /Effexor®	
	Voriconazole /VFend®	
	Ziprasidone /Geodon®	

References:

1. Physician's Desk Reference 2002
2. Facts and Comparisons (update to June 2005)
3. The Pharmacological Basis of Therapeutics 9th Edition, 1996

APPENDIX D: NEW YORK HEART ASSOCIATION CLASSIFICATION OF CARDIAC DISEASE

Class	Functional Capacity	Objective Assessment
I	Subjects with cardiac disease but without resulting limitations of physical activity. Ordinary physical activity does not cause undue fatigue, palpitation, dyspnea, or anginal pain.	No objective evidence of cardiovascular disease.
II	Subjects with cardiac disease resulting in slight limitation of physical activity. They are comfortable at rest. Ordinary physical activity results in fatigue, palpitation, dyspnea, or anginal pain.	Objective evidence of minimal cardiovascular disease.
III	Subjects with cardiac disease resulting in marked limitation of physical activity. They are comfortable at rest. Less than ordinary activity causes fatigue, palpitation, dyspnea, or anginal pain.	Objective evidence of moderately severe cardiovascular disease.
IV	Subjects with cardiac disease resulting in inability to carry on any physical activity without discomfort. Symptoms of heart failure or the anginal syndrome may be present even at rest. If any physical activity is undertaken, discomfort is increased.	Objective evidence of severe cardiovascular disease.

APPENDIX E: PATIENT'S MEDICATION DIARY

EXPANSION PHASE, COHORT A, CYCLE 1

Today's date _____

Agent: Pazopanib, ARQ 197

Patient Name _____

Patient Study ID _____

INSTRUCTIONS TO THE PATIENT:

1. Complete one form for each cycle of treatment.
2. **Starting on day 1**, you will take **pazopanib** once each day in the morning either 1 hour before or 2 hours after a meal with 1 cup of water.
Dose: _____. Take ____ 200 mg tablets and ____ 400 mg tablets every day. You should swallow the tablets whole.
Do not chew, crush, or break the tablets.
3. **Starting on day 8**, you will take **ARQ 197** twice each day, about 12 hours apart, with food. You should swallow the tablets whole. **Do not chew, crush, or break the tablets. You will not take ARQ 197 on days 1-7 of cycle 1.**
Morning dose: _____. Take ____ 120 mg tablets. Evening dose: _____.
Take ____ 120 mg tablets.
4. Record the date, the number of tablets of each size you took, and when you took them.
5. If you have any comments or notice any side effects, please record them in the Comments column.
6. Please bring this form and your bottles of **pazopanib and ARQ 197** tablets when you return for each appointment.
7. You should measure your own blood pressure at home at least once a day (preferably twice a day). If your systolic pressure (top number) is greater than 150 or your diastolic blood pressure (bottom number) is greater than 90, re-measure your blood pressure 1 to 4 hours later. If your systolic pressure is still greater than 150 or your diastolic blood pressure is still greater than 90, please contact your study team for instructions. You should also call the research team if you experience any symptoms of high blood pressure, such as chest pain, shortness of breath, headache, blood in the urine, or double vision.

CTEP Protocol #8880
 Clinical Center Protocol #: 12-C-0009

CTEP-assigned Protocol #8880 Local Protocol # _____
--

Today's date _____
 Patient Name _____

Agent: Pazopanib, ARQ 197
 Patient Study ID _____

Day	Date	Pazopanib		ARQ 197				Blood Pressure AM	Blood Pressure PM	Comments	
		Time of dose	# of tablets taken		Time of morning dose	# of tablets taken	Time of evening dose				# of tablets taken
			200 mg	400 mg							
1				-----	-----	-----	-----				
2				-----	-----	-----	-----				
3				-----	-----	-----	-----				
4				-----	-----	-----	-----				
5				-----	-----	-----	-----				
6				-----	-----	-----	-----				
7				-----	-----	-----	-----				
8											
9											
10											
11											
12											
13											
14											
15											
16											
17											
18											
19											
20											
21											
22											
23											
24											
25											
26											
27											
28											

Patient's signature _____

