5.1.2 Expansion Phase

Once the MTD is established, an additional cohort of patients will initially be treated with pazopanib alone, and tumor biopsies will be obtained to assess target inhibition, as outlined below. Tumor biopsies will be mandatory during the expansion phase of the study. Biopsies will be obtained at the time points outlined below. Depending on the results obtained from the tumor biopsies in the first few patients, the timing of the biopsy can be adjusted, but the number of tumor biopsies and the procedure will not change. Any change in the timing of the tumor biopsy will be discussed with the patient prior to obtaining informed consent.

The cohort and dosing regimens after establishment of the MTD are described below. When administered as a single agent during the expansion phase, the dose of pazopanib will correspond to the dose determined for the combination MTD if the MTD is determined at dose level 5 (ARQ 197 360 mg BID/pazopanib 800 mg QD) or 6 (ARQ 197 360 mg BID/pazopanib 600 mg QD). Otherwise, the dose of pazopanib will be determined after discussion with CTEP. Once the MTD is established, the data will be discussed with CTEP prior to proceeding with accrual for the expansion phase.

Cohort A (12 patients): Pazopanib will be given once daily as single agent from cycle 1 day 1 to day 7. Tumor biopsy will be done before drug administration on study (baseline) and on cycle 1 day 8, 8-12 hours after pazopanib administration. **After** the tumor biopsy, patients will start to receive ARQ 197 in addition to pazopanib at the combination MTD.

Twelve evaluable patients with both pre- and post-treatment biopsies will be treated initially in Cohort A. Mean increases in MET and pMET in these 12 patients will be measured to assess whether or not they are statistically significant.

For the purposes of final analysis of the expansion phase, only patients with paired tumor biopsies will be considered evaluable. Patients with fewer than the 2 required biopsies will not be considered evaluable for the expansion phase and will need to be replaced in the accrual scheme of the expansion phase. If a patient has a dose-limiting toxicity (DLT) with the single lead-in agent pazopanib in the expansion cohort, the patient will be taken off treatment.

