9.1.2 Tumor Biopsies

9.1.2.1 Timing of tumor biopsies

Biopsies will be collected optionally during the escalation phase:

- before drug administration on study (baseline), and
- on cycle 1 day 8; 8-12 hours after the Day 7 evening dose of ARQ 197 (the morning dose of ARQ 197 will be taken 1 hour after pazopanib)

Biopsies will be mandatory during the expansion phase:

Cohort A

- before drug administration on study (baseline), and
- on cycle 1 day 8, 8-12 hours after pazopanib and before the first dose of ARQ 197

The C1D8 biopsy can be collected on C1D7 for scheduling reasons.

Tumor biopsy requires fasting during at least 8 hours after food taken with ARQ 197.

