9.2.1.2 Expansion Phase

Blood samples for PK analysis will be collected prior to drug administration and at multiple time points after drug administration beginning on D1 and D7 of cycle 1 only. Pazopanib will be taken on an empty stomach 1 hour before a meal and ARQ 197 will be taken with food.

Cohort A:

D1: pre-dose, and 1, 2, 4, 6, and 12 hours after administration of pazopanib.

D7: pre-dose, and 1, 2, 4, and 6 hours after administration of pazopanib.

The PK studies are mandatory and will be required for every patient. The total volume of blood collected for PK studies during the initial treatment cycle is expected to be < 70 mL per patient. Based on results from initial measurements, sampling times may be adjusted, but neither the total number of samples nor the total amount of blood drawn per patient will be increased. Samples will be collected in lavender-top (EDTA) tubes with 6 mL (3 mL for day 1 in Cohort A of the expansion phase) of blood per sample. It is important to fill the Vacutainer tubes to the specified collection volume. The tube containing blood for plasma preparation will be gently inverted 10 times to ensure

thorough mixing of anticoagulant and blood, then placed in a cool box containing crushed ice and/or water.

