at the start of each cycle (\pm 1 day for scheduling conflicts). For patients who have been on study for 6 or more cycles and are tolerating treatment well, lab tests may be performed once every 2 cycles (every 2 months). Serum liver tests (AST, ALT, serum bilirubin) will also be performed during weeks 3, 5, 7 (*can be collected by patients' local physician), and 9; thereafter, monitoring will occur at months 3 and 4, and as clinically indicated. Periodic monitoring will continue after month 4.

- e: Evaluation of urine protein/creatinine ratio should occur at baseline, on C1D8, then at the start of each cycle (\pm 1 day for scheduling conflicts), and as clinically indicated. If patient has urine protein/creatinine ratio $>1+$, obtain a 24 hour urine for protein and creatinine clearance.
- f: EKG will be performed at baseline, on C1D1 (3-6 hours after the morning dose of pazopanib), on C1D8 (3-6 hours after pazopanib), on *C2D1 (3-6 hours after the morning dose of ARQ 197), and as clinically indicated.
- g: Serum or urine pregnancy test (women of childbearing potential) within 1 week prior to enrollment.
- h: Tumor biopsies are mandatory in the expansion phase: at baseline and on C1D8, 8-12 hours after pazopanib before the first dose of ARQ 197.
- i: Samples will be obtained at the following time points: at baseline, on C1D1 (2, 4, and 6 hours after pazopanib), on C1D8 (pre-drugs), and on C2D1 (pre-drugs).
- j: A sample for the PG study will be obtained at baseline.
- k: Blood samples for PK will be collected from all patients during cycle 1 only on D1 and D7 as specified in [Section 9.2.1.2](#).

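### The Cohort A cycle 1 diary opens a morning ARQ 197 dose on day 8, although the protocol body requires the day 8 biopsy to come before any ARQ 197

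*Combined protocol and SAP*

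**What the plan says.** The protocol body is consistent about the order of events in Cohort A.

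- Section 5.1.2 sets the second biopsy on cycle 1 day 8, 8 to 12 h after pazopanib. Only after it, "patients will start to receive ARQ 197 in addition to pazopanib at the combination MTD".
- Section 9.1.2.1 times the biopsy "on cycle 1 day 8, 8-12 hours after pazopanib and before the first dose of ARQ 197".
- Section 10.2, footnote h, repeats this: "on C1D8, 8-12 hours after pazopanib before the first dose of ARQ 197".
- The expansion schema, footnote b, gives the same order without the 8 to 12 h window.

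Section 9.1.2.1 adds two conditions: "The C1D8 biopsy can be collected on C1D7 for scheduling reasons", and "Tumor biopsy requires fasting during at least 8 hours after food taken with ARQ 197".

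Appendix E is the patient's own form, headed for the expansion phase, Cohort A, cycle 1. Item 2 puts pazopanib in the morning, 1 h before or 2 h after a meal. Item 3 starts ARQ 197 on day 8, "twice each day, about 12 hours apart, with food", with a morning and an evening dose to fill in. Its only restriction is "You will not take ARQ 197 on days 1-7 of cycle 1". In the grid, the ARQ 197 cells are dashed out for days 1 to 7 and open from day 8. The diary does not mention the biopsy.

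**The concern.** The diary and the body agree that ARQ 197 starts on day 8. They disagree on what happens within that day. Pazopanib is a morning drug in the diary, so a biopsy 8 to 12 h later falls in the afternoon or evening. An ordinary morning ARQ 197 dose comes first. The patient would have complied with the diary and broken the protocol, and Section 7.3.4.2 makes every protocol deviation reportable to the IRB.

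At stake is what the second biopsy means. Cohort A has a week of pazopanib alone so that this sample shows the effect of pazopanib on MET and phospho-MET. Section 1.1 lists change in these markers as a primary objective, and Section 13.1 assesses the mean increase in 12 patients. Section 2.4.1.1 describes the aim as measuring MET activation by pazopanib and its blunting by ARQ 197. A sample taken after ARQ 197 mixes the two.

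**Working it through.** The plan states no figure on this point, so there is none to reproduce. The check compares clock times.

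**Inputs**
- Biopsy at time b after pazopanib, with b from 8 to 12 h (5.1.2, 9.1.2.1, 10.2 footnote h).
- Morning ARQ 197 at time a relative to pazopanib. It is taken with food, and the diary allows a meal 1 h after pazopanib (a = +1) or 2 h before it (a = -2). The +1 h spacing is also the one Section 9.2.1.1 uses on the escalation-phase PK days. Which meal carries the dose is an assumption, so both are shown.
- Day 8 EKG 3 to 6 h after pazopanib (Section 5).
- Fast of at least 8 h after food taken with ARQ 197 (9.1.2.1).

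**Time from ARQ 197 to biopsy** = b - a
- a = +1: 8 - 1 = 7 h to 12 - 1 = 11 h.
- a = -2: 8 + 2 = 10 h to 12 + 2 = 14 h.

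Any dose with a below 8 h precedes the whole biopsy window, so the conflict does not depend on the exact spacing.

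**Does the fasting rule block the error?** The earliest biopsy it permits is at a + 8.
- a = +1: 1 + 8 = 9 h. A biopsy at 9 to 12 h after pazopanib, which is 8 to 11 h after ARQ 197, is still allowed.
- a = -2: -2 + 8 = 6 h, before the window opens, so there is no constraint.
- A dose as late as 12 - 8 = 4 h after pazopanib satisfies both rules.

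The fast does not prevent the wrong order.

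**Does the EKG catch it in time?** Time from ARQ 197 to EKG:
- a = +1: 3 - 1 = 2 h to 6 - 1 = 5 h.
- a = -2: 3 + 2 = 5 h to 6 + 2 = 8 h.

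In both cases the dose has already been taken. The EKG visit could reveal the error but not prevent it.

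**Day 7 biopsy.** ARQ 197 starts the next day, so the diary and the body agree.

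**What the body implies for day 8.** Assume pazopanib at 08:00 (the documents give no clock time). The biopsy then falls at 16:00 to 20:00. For pazopanib between 06:00 and 10:00 the range is 14:00 (06:00 + 8 h) to 22:00 (10:00 + 12 h). Only an evening ARQ 197 dose can follow. The open morning cell is therefore wrong for the default biopsy day.

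**The case against.** The strongest reply is that this is a gap in a patient form, and that the visit schedule largely covers it. The day 8 blood sample must be drawn before either drug (9.1.3; 10.2 footnote i), so a compliant patient reaches staff undosed. The same day has an examination and an EKG timed to pazopanib. The PK/PD group has at least 24 h notice of a biopsy (9.1.1), and each biopsy needs its own signed consent (9.1.2.2). On day 7 staff see the patient for PK sampling: "D7: pre-dose, and 1, 2, 4, and 6 hours after administration of pazopanib". The consent pages are not in the text reviewed and may tell patients what to do on biopsy day. The documents also do not say whether ARQ 197 is in the patient's hands before the biopsy.

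Most of this stands, and it lowers the chance of error. It does not remove the conflict. The pre-drug draw controls only what comes before it. In the sections available, none of these contacts carries an instruction to withhold the morning dose until the biopsy is done, and the one form the patient takes home invites that dose.

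Three stronger readings are tempting and are not supported.

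- **That the design is at fault.** The order of biopsy then ARQ 197 is sound and is stated the same way throughout the body.
- **That the bias can be sized, for instance as up to one twelfth of the mean change per affected pair.** That needs a cap at full cancellation of the rise, which the documents do not give. In the Figure 6 legend, intact MET in the MKN45 combination group fell below vehicle. The pY1235-MET/MET ratio in that model did not change significantly under any regimen. The blunting in SNU5 followed co-administration, whereas the error here is one ARQ 197 dose after a week of pazopanib alone. The number of affected pairs is also unknown.
- **That the evaluability rule would admit wrong-order pairs.** Section 5.1.2 first defines the second Cohort A biopsy as preceding ARQ 197 and then requires both biopsies. The natural reading already excludes such a pair.

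**Conclusion.** Appendix E is wrong as written. It conflicts with the schema and with Sections 5.1.2, 9.1.2.1 and 10.2 for the default day 8 biopsy. Followed literally, it puts ARQ 197 about 7 to 11 h or 10 to 14 h before the biopsy, depending on whether the dose goes with a meal 1 h after or 2 h before pazopanib.

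An effect on the sample is plausible. Section 2.3.2 gives an ARQ 197 Tmax of 2 to 6 h, and Section 2.3.1 reports c-MET suppression in cells lasting at least 8 to 12 h after withdrawal. Its size cannot be estimated from the documents and may be zero. Section 2.4.1.1 treats phospho-MET as exploratory and calls the drug's effect on constitutively phosphorylated MET unclear. Section 13.1 attaches no significance level or decision rule to the comparison.

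Severity is low. The correction is worth making because the error sits in a patient instruction and touches the sample behind a primary objective.

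**What to change.** In the Appendix E grid, dash out the day 8 morning ARQ 197 cell, and let staff reopen it if the biopsy was done on day 7. Add one line under item 3: *On day 8 do not take ARQ 197 until after your biopsy.*

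Optionally, and only as a clarification, state in Section 5.1.2 that the second required Cohort A biopsy must precede any ARQ 197. This can be checked from the dose times in the diary and the collection times on the specimen labels (9.1.4), both already recorded.

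The cost is one diary line and one cell, with no new data and no design change. For a day 8 biopsy no dose is lost that the protocol body allows. A patient biopsied on day 7 could miss one morning dose if the cell is not reopened.
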